18.1.2. PHARMACOKINETIC PARAMETERS

Subjects with partial data will be evaluated on a case-by-case basis to determine if sufficient data are available for reliable estimation of PK parameters.

For PK parameter calculations following IV dose:

- Concentrations that are BLQ or missing at pre-dose or the beginning of the curve will be set to zero.
- Any other BLQ concentrations will be assigned a value of zero if they precede quantifiable samples in the initial portion of the profile.
- A BLQ value that occurs between quantifiable data points, especially prior to C_{max}, will be evaluated to determine if an assigned concentration of zero makes sense, or if exclusion of the data is warranted.
- Following C_{max}, BLQ values embedded between two quantifiable data points will be treated as missing when calculating PK parameters.
- If a BLQ value occurs at the end of the collection interval (after the last quantifiable concentration), it will be set to zero.
- If consecutive BLQ concentrations are followed by quantifiable concentrations in the terminal portion of the concentration curve, these quantified values will be excluded from the PK analysis by setting them to missing, unless otherwise warranted by the concentration-time profile.

The following PK parameters will be calculated following IV administration of ANB019 by noncompartmental methods, using actual elapsed time from dosing.

C _{max}	Maximum observed concentration, obtained directly from the observed concentration versus time data.	
t _{max}	Time of maximum observed concentration, obtained directly from the observed concentration versus time data.	
t _{1/2}	Apparent terminal half-life (h), determined as $(\ln 2/\lambda z)$	
CL	Systemic clearance (L/h) calculated as dose/AUC _(0-last)	
Vz	Volume of distribution (L) during terminal phase, estimated by dividing the systemic clearance by λz .	
λz	Apparent terminal rate constant (1/h), determined by linear regression of the terminal points of the log-linear concentration-time curve.	
AUC(0-last)	Area under the concentration-time curve (AUC) from time zero (pre-dose) to time of last quantifiable concentration, calculated by linear up/log down trapezoidal summation.	
AUCoverall	Area under the concentration-time curve (AUC) from time zero (pre-dose) on Day 1 (IV dose) to time of last quantifiable concentration following Day 87 SC dose	
Note: The dat	Note: The data from Day 1 to Day 29 pre-dose will be used to calculate the first 7 parameters.	

Details of any future population PK modeling and potential pharmacodynamic (PD) and/or efficacy/safety correlative exploratory analyses will be described in a separate modeling and simulation analysis plan that will be considered separate from this study SAP. Results from any population PK analysis and correlation with PD/efficacy/safety results will be presented in a PK modeling and simulation report that will be separate from the main clinical study report.

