### 2.2.1 Nonclinical Studies

ANB019 has strong inhibitory activity of human as well as the cynomolgus monkey IL-36R. Nonclinical data obtained from studies with ANB019 in primary human and cynomolgus monkey cells and from in vivo non-human primate studies demonstrated that:

- ANB019 shows reactivity with human and cynomolgus monkey IL-36R (dissociation constant [REDACTED]), but not with mouse or rat IL-36R.
- In primary human and cynomolgus monkey cell populations, keratinocytes, peripheral blood mononuclear cells and human whole blood, ANB019 inhibits IL-36R-mediated release of interleukin-8 (IL-8).
- The observed serum half-life of ANB019 in cynomolgus monkeys was 304 hours after single IV dose administration, and 310 hours after single SC dose administration at 10 mg/kg, with

bioavailability approximately 76% consistent with the anticipated PK characteristics for a human IgG4 scaffold mAb in the monkey.

- Repeat-dose, Good Laboratory Practice toxicity and toxicokinetic studies of 4 and 13 weeks in duration have been conducted with ANB019 administered by weekly SC and IV injection to cynomolgus monkeys. There were only minor treatment-related injection site findings in the 4-week repeat-dose study. Treatment-related effects in the 13-week toxicity study included increased observations of nonformed feces and prolapsed rectum, and protozoa in the stomachs of monkeys, the latter being consistent with the mechanism of action of an immune-modulator in cynomolgus monkeys (Augey 2006). These studies established a no observed adverse effect level for males at 60 mg/kg/dose administered IV and for females at 60 mg/kg/dose administered SC after 13 weeks of dosing.

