#### **4.3 Justification for Dose**

ANB019 will be administered as a single IV dose of 750 mg followed by 3 doses of 100 mg SC administered on Days 29, 57, and 85.

The doses selected for this study have demonstrated favorable safety profile and prolonged pharmacodynamic activity in a Phase I study (ANB019-001). A loading dose of 750 mg IV will be administered on Day 1 to enable steady state concentration to be reached faster at initiation of the ANB019 100 mg SC dose. The 12-week treatment duration is expected to provide adequate time to assess the safety and efficacy of ANB019 in subjects with GPP.

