### **Protocol ANB019-002: Amendment 2, 27 July 2018**

#### **Replaces: Amendment 1, 15 January 2018**

Section 1.1 Synopsis and Section 4.1 Overall Design:

- Description of Change: Text revised to remove a minimum of 7 days screening period requirement and updated ‘up to 28 days’.
- Purpose of Change: To simplify enrollment of newly diagnosed subjects.
- Description of change: Updated the number of Investigators and number of study centers from 3 to 5.
- Purpose of change: To reflect the updated number of Investigators and study centers (administrative change).

Section 2.2 Background (Clinical studies).

- Description of Change: Added the percentage for mild and moderate TEAEs and details about 1 severe AE.
- Purpose of Change: To reflect the updated Phase I Study results (ANB019-001, SAD part).

Section 2.2 Background and Section 2.3 Benefit/Risk Assessment:

- Description of Change: Text revised to include SAD (PP) safety and MAD (healthy volunteers) safety and PK data from the Phase I study (ANB019-001) in healthy volunteers and PP subjects.
- Purpose of Change: To reflect New safety and PK data from the Phase I study (ANB019-001).

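### SAP 18.1.2 computes IV clearance from AUC(0-last) to Day 29 without the extrapolated area, so CL and Vz are biased upward by a factor that depends on half-life

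*SAP*

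**What the plan says.** The parameter table in SAP 18.1.2 lists, in order, Cmax, tmax, t1/2, CL, Vz, λz, AUC(0-last) and AUCoverall. Clearance is "Systemic clearance (L/h) calculated as dose/AUC _(0-last"). Vz is "estimated by dividing the systemic clearance by λz". AUC(0-last) stops at the last quantifiable concentration and uses the linear up/log down rule. The note under the table reads "The data from Day 1 to Day 29 pre-dose will be used to calculate the first 7 parameters", which covers everything except AUCoverall. λz comes from log-linear regression on the terminal points of the same window. Neither document defines AUC(0-inf) or percent extrapolated.

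SAP 18.4 summarizes the IV parameters, allows summaries by ADA status, and gives no summary when fewer than three subjects contribute. Protocol 9.4.7.1 names only Cmax, Tmax and AUC and leaves room for others.

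**The concern.** Dose/AUC equals systemic clearance after a single dose only if the AUC runs to infinity. Cutting the area at Day 29 makes the denominator too small whenever drug is still present. Protocol 4.3 implies that it is: the IV dose is given "to enable steady state concentration to be reached faster at initiation of the ANB019 100 mg SC dose". No amount is stated.

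The error varies with each subject's half-life and last sample time, so a reader cannot divide out one constant. It can therefore distort comparisons between subjects, including the optional summary by ADA status.

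No other text repairs the formula. The option of extra parameters in Protocol 9.4.7.1 does not change how CL is computed. The clause "Subjects with partial data will be evaluated on a case-by-case basis" concerns incomplete profiles, and complete ones are biased too. AUCoverall includes the SC doses and is not used for CL. Population PK is deferred to a possible separate plan and report.

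**Working it through.** The plan states no CL, Vz or AUC value, so there is no figure to reproduce. The check sizes the error from the SAP's definitions.

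**Inputs**
- Window: Day 1 to Day 29 pre-dose, 28 days = 672 h (SAP 18.1.2).
- Sampling: pre-dose, 1 h and 4 h on Day 1, then Days 3, 8, 15, 22 and 29, that is 0, 1, 4, 48, 168, 336, 504 and 672 h, with a 1-hour infusion (Protocol Table 2).
- Half-life: Protocol 2.2.1 gives monkey values only: "The observed serum half-life of ANB019 in cynomolgus monkeys was 304 hours after single IV dose administration"; its figure for the SC route is 310 h. No human value was in the text available. The Amendment 2 log ("Text revised to include SAD (PP) safety and MAD (healthy volunteers) safety and PK data from the Phase I study") points to Protocol 2.2 and 2.3; if a human half-life stands there, it should go into the formula below. The values 7, 14, 21 and 28 days are assumptions.

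**Formulas** (one-compartment decline)
- Omitted share of AUC(0-inf): f = 2^(−28/t½), t½ in days.
- CL(SAP)/true CL = AUC(0-inf)/AUC(0-last) = 1/(1 − f).
- Vz = CL/λz, so for a given λz it has the same factor.

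Example at 304 h = 12.67 d: f = 2^(−28/12.67) = 0.216; 1/(1 − 0.216) = 1.276, or +28%.

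The fourth column applies linear up/log down to noise-free one-compartment profiles at the Table 2 times. The last adds an assumed distribution phase (40% or 60% of C0, half-life 1 or 3 days).

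| Half-life | f | CL and Vz factor | Table 2 times | With distribution phase |
|---|---|---|---|---|
| 7 d (assumed) | 0.0625 | 1.067 | +6.7% | +2.2% to +4.6% |
| 304 h = 12.67 d (monkey IV) | 0.216 | 1.276 | +27.6% | +17.7% to +24.1% |
| 310 h = 12.92 d (monkey SC) | 0.223 | 1.286 | +28.7% | +18.5% to +25.1% |
| 14 d (assumed) | 0.250 | 1.333 | +33.4% | +22.0% to +29.6% |
| 21 d (assumed) | 0.397 | 1.658 | +65.9% | +46.8% to +60.6% |
| 28 d (assumed) | 0.500 | 2.000 | +100.1% | +73.6% to +93.4% |

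The omitted share is below 5% only if t½ is under 28 × ln 2/ln 20 = 6.5 days.

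**Timing of the last sample.** At 304 h, the ±2-day Day 29 window gives +31.8% (day 26 after dosing), +27.6% (28) and +24.0% (30). A profile ending on Day 22 (21 days after dosing), if accepted under the case-by-case review, gives +46.4%.

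**Two subjects with assumed half-lives of 14 and 28 days** (factors 1.333 and 2.000; V = CL × t½/ln 2)
- Equal volumes: the true 2.0-fold CL difference is reported as 2.0 × 1.333/2.000 = 1.33-fold, and equal Vz as 2.000/1.333 = 1.5-fold different.
- Equal CL (volumes differ 2-fold): reported as 1.5-fold different.
- Twice the CL in the subject with the longer half-life (volumes differ 4-fold): the true 2.0-fold difference is reported as 2.0 × 2.000/1.333 = 3.0-fold.

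**Corrected formula.** With AUC(0-inf) = AUC(0-last) + Clast/λz and λz from the last three samples (an assumption), one-compartment CL and Vz return to 1.000 of true. In the distribution-phase runs the CL error is −2.9% to +7.4%.

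**With noise** (one-compartment, assumed 20% log-normal residual error, 8,000 profiles per setting)

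| | 304 h | 28 d |
|---|---|---|
| Per-subject RMSE, SAP formula | 29% | 100% |
| Per-subject RMSE, dose/AUC(0-inf), profiles with positive λz | 16% | 37% |
| No positive λz | 0.4% | 11.4% |
| Extrapolated share above 20% | 56% | 98% |
| Extrapolated share above 30% | 22% | 85% |

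**The case against.** The strongest case against is about weight. The study is exploratory, CL and Vz are SAP additions, no decision depends on them, and no comparison of CL between subjects is firmly planned. Cmax, tmax, λz, t1/2 and AUC(0-last) are unaffected. Concentrations and individual parameters are listed, so CL can be recomputed. The SAP also states its denominator openly, so one could call this a labelling fault. All of that stands and limits the consequence. It does not make dose/AUC(0-last) systemic clearance.

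The second argument is that the remedy adds noise. With 20% residual error, the spread due to assay noise alone is about 9% CV for the SAP formula at every half-life tried. For dose/AUC(0-inf) it is about 17% at 304 h and 38% at 28 days. That is true and is a real cost. Total error is still lower with the corrected formula at every half-life tried, although its RMSE excludes profiles without a positive λz.

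Third, the sizes are not anchored to GPP subjects, and enlarged or spurious CL differences require unequal volumes. Both are correct: the sizes are illustrations, and the volume premise is stated with each case. Neither changes the direction of the bias.

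**Conclusion.** The concern holds. As written, the SAP overstates CL and Vz by AUC(0-inf)/AUC(0-last) after a single IV dose. The upward direction and the common factor need only the SAP's definitions and drug remaining at the last sample; the bias is negligible if concentrations become unquantifiable well before Day 29. The size for this trial cannot be fixed from the text available. In the one-compartment case it is +28% at the monkey IV half-life and runs from +7% to +100% over assumed half-lives of 7 to 28 days; a distribution phase lowers these somewhat. This should be corrected before database lock, but it does not touch the primary endpoint or any decision rule.

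**What to change.** In SAP 18.1.2:
- Add AUC(0-inf) = AUC(0-last) + Clast/λz and %AUC extrapolated = 100 × (Clast/λz)/AUC(0-inf), both from Day 1 to Day 29 pre-dose data.
- Define CL = dose/AUC(0-inf) and keep Vz = CL/λz.
- Reword the note so that it covers every parameter except AUCoverall.
- Set, before database lock, the extrapolated percentage above which CL and Vz are flagged.
- Where λz or the extrapolation is unreliable, do not report systemic clearance for that subject; label the value dose/AUC(0-Day 29).

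**Cost:** two added parameters and one changed formula, all standard non-compartmental output, with no new samples. The downside is a noisier CL and possible flagging of some or most of the roughly 10 subjects. The minimum of three subjects in SAP 18.4 could then leave no CL or Vz summary. The relabelled value remains available in that case.

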**Table 2 PK/ADA Sample Collection and Timepoints**

Study Visit	PK Sample Timepoint Plasma	ADA Sample Timepoint Serum
Day 1 a	Pre-dose	Pre-dose
	1 hr (± 10 min) post-dose	
	4 hrs (± 10 min) post-dose	
Day 3	Anytime	
Day 8	Anytime	
Day 15	Anytime	
Day 22	Anytime	
Day 29	Pre-dose	Pre-dose
Day 43	Anytime	
Day 57	Pre-dose	Pre-dose
Day 71	Anytime	
Day 85	Pre-dose	Pre-dose
Day 113	Anytime	
Day 141	Anytime	
Day 169	Anytime	Anytime

ADA = anti-drug antibodies; hr(s) = hour(s); min = minutes; PK = pharmacokinetic.

a Infusion of study treatment will take approximately 1 hour. Therefore, the 1-hour PK sample collection on Day 1 must start immediately at the end of the infusion. The 4-hour collection must occur exactly 3 hours after the 1-hour collection is completed.

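### Half-life, λz and Vz come only from the first 28 days; the planned Day 113, 141 and 169 samples could add a steadier terminal estimate at almost no cost

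*SAP*

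**What the plan says.** SAP 18.1.2 lists the non-compartmental parameters after the IV dose. λz is "determined by linear regression of the terminal points of the log-linear concentration-time curve", and half-life is "Apparent terminal half-life (h), determined as" ln 2/λz. Vz is clearance divided by λz. A note under the table adds: "The data from Day 1 to Day 29 pre-dose will be used to calculate the first 7 parameters". Those seven are Cmax, tmax, t1/2, CL, Vz, λz and AUC(0-last). The section gives no start day, minimum number of points or minimum span for the terminal regression.

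Protocol 4.3 gives one IV dose on Day 1 "followed by 3 doses of 100 mg SC administered on Days 29, 57, and 85". Protocol Table 2 schedules PK samples on Day 1 (pre-dose, 1 h, 4 h), on Days 3, 8, 15, 22 and 29 (pre-dose), and later on Days 113, 141 and 169. In the non-compartmental analysis only AUCoverall runs past Day 29.

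The only half-lives in the supplied text are from cynomolgus monkeys, in Protocol 2.2.1: "304 hours after single IV dose administration, and 310 hours after single SC dose administration".

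**The concern.** A terminal slope fitted over few half-lives is imprecise. If the fit starts while drug is still distributing, it is also too steep, so the half-life comes out short. Once the early distribution samples are set aside, the Day 1 to 29 window leaves four points at most from Day 8 on.

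The trial already collects three samples with no dose in between, spread over 56 days, and the SAP does not use them for this purpose. At stake are the reported t1/2, λz and Vz from about 10 subjects. These are secondary and descriptive, but a figure labelled terminal half-life tends to be carried into later planning.

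**Working it through.** The documents state no precision figure for the PK parameters, so there is nothing of theirs to reproduce.

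**Half-lives covered** (window length divided by half-life, monkey values):
- Days 8 to 29: 21 d = 504 h; 504/310 = 1.63 and 504/304 = 1.66.
- Days 3 to 29: 26 d = 624 h; 2.01 to 2.05.
- Full 28 days: 672 h; 2.17 to 2.21.
- Days 113 to 169: 56 d = 1344 h; 4.34 to 4.42.

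With an assumed human half-life of 14, 21 or 28 days, Days 8 to 29 cover 1.50, 1.00 or 0.75 half-lives.

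**Slope precision.** For least squares on log concentration, SE(λz) = σ/√Sxx, where Sxx is the sum of squared deviations of the sampling days from their mean.
- Days 8, 15, 22, 29 (mean 18.5): 2 × 10.5² + 2 × 3.5² = 245 d².
- Days 113, 141, 169 (mean 141): 2 × 28² = 1568 d².
- Ratio of standard errors with equal σ: √(1568/245) = 2.53.

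**Sensitivity of that ratio**

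| Change | Ratio |
|---|---|
| Early window Days 3–29 (Sxx 437.2) | 1.89 |
| Early window Days 15–29 (Sxx 98) | 4.00 |
| Visits at the ±2-day limits on Days 113 and 169 | 2.35 to 2.71 |
| Day 169 below quantitation (Sxx 392) | √(392/245) = 1.26 |
| Late log error doubled | 2.53/2 = 1.26 |
| Late log error 2.5 times larger | 1.01 |

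As an example, assume 10% log error and a half-life of 21 d, so λz = 0.693/21 = 0.0330 per day. The CV of λz is (0.1/√245)/0.0330 = 19.4% from Days 8 to 29 and (0.1/√1568)/0.0330 = 7.7% from Days 113 to 169.

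**Bias, under an assumed model.** Two-compartment linear antibody kinetics: V1 3–3.2 L, Q 0.5–0.6 L/d, V2 2.5–3 L, CL 0.15–0.35 L/d, SC ka 0.25/d, F 0.7. True half-life is about 13 to 30 d, with 15% residual CV. None of these inputs is in the documents.

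| Window | CV of λz | Bias in λz |
|---|---|---|
| Days 3–29 | not tabulated | +32 to +60% |
| Days 8–29 | 18 to 42% | +9 to +15% |
| Days 15–29 | 28 to 67% | +1 to +2% |
| Days 113–169 | 7 to 17% | within 1% |

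For a true half-life of about 23 d, the 5th to 95th percentile range of one subject's estimate is 14 to 39 d from Days 8 to 29 and 19 to 30 d from Days 113 to 169.

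**The case against.** The planned window is not arbitrary. Protocol 3.0 ties the PK parameters to the first dose and names only Cmax, Tmax and AUC, with others as appropriate. The SAP labels its parameters as following IV administration, calls the half-life apparent, and leaves any population PK modelling to a separate plan. A slope after three SC doses is an additional parameter. This stands, and it is why the point is not an inconsistency. It does not prevent the addition: Protocol 9.4.7.1 allows further parameters, and AUCoverall already goes past the first dose.

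The size depends on unknowns. The supplied text gives no human half-life, assay limit or residual error. Late concentrations are far lower: in a simple one-compartment calculation with the monkey SC bioavailability of 76%, the fall from Day 29 to Day 169 is about 29-fold at a 21-day half-life and 155-fold at 12.7 days. Similar IV and SC half-lives in monkeys at one dose do not establish linear kinetics at low human concentrations. No ADA sample is scheduled between Day 85 and Day 169. All of this stands, and is the reason to report both estimates. In the assumed model, doubling the late error to 30% still leaves a late root mean square error of 14 to 33%, against 20 to 45% for Days 8 to 29 at 15%.

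Three points leave 1 residual degree of freedom. A subject's own 95% interval would use t = 12.71 instead of 4.30, giving an early-to-late width ratio of 2.53 × 4.30/12.71 = 0.86, so the late interval would be about 17% wider. That is correct, but SAP 18.4 plans summaries across subjects and no individual intervals. What matters there is the sampling error of each point estimate.

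A reader might infer three stronger things:
- *The IV window covers only one to one and a half half-lives.* That needs a human half-life of about 14 to 21 d, which the supplied text does not give.
- *The late window is 2.5 times better without qualification.* The sensitivity table shows otherwise.
- *The planned half-life is necessarily biased short.* The SAP does not fix the points. Starting at Day 15 removes nearly all the bias in the assumed model, at the price of a larger CV.

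**Conclusion.** The point holds as a cheap improvement to a secondary, descriptive analysis. λz, t1/2 and Vz rest on a short window with no stated rule for its terminal points, while a longer dose-free decline is sampled and left unused for them.

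The gain in slope standard error is about 2.5-fold against Days 8 to 29, and 1.9 to 4.0 by early window. It assumes equal log error, three quantifiable late samples and linear kinetics, and falls to about 1.3 if Day 169 is below quantitation or late error doubles. The overestimate of λz by about 9 to 15% from Days 8 to 29 rests wholly on the assumed two-compartment model. The documents do not support calling the Day 1 to 29 window an error, because it follows the protocol's first-dose scope.

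**What to change.** In SAP 18.1.2:
- For subjects who received the Day 85 dose and have quantifiable samples on all of Days 113, 141 and 169, add λz and t1/2 from those three samples.
- Relabel the Day 1 to 29 values as IV-phase, keep them in the summary for all subjects, and show the two sets side by side.
- For each estimate, report the span and the number of points used.
- State which λz enters Vz.

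Do not drop IV-phase values because the fit spans too few estimated half-lives. Over 21 days, a two-half-life rule keeps only estimates of 21/2 = 10.5 d or less. In the assumed model with true half-lives of 13.5 to 29 d, about 0 to 15% of subjects would remain, with a median near 10 d, so the rule would select the most underestimated values.

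The cost is SAP wording and one more non-compartmental run on samples already planned. The limits are no late estimate for Week 4 nonresponders or subjects with late samples below quantitation, 1 residual degree of freedom per subject, and a late slope that ADA or non-linear clearance could alter.

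While editing the table, reconcile the AUCoverall definition, which runs "to time of last quantifiable concentration following Day 87 SC dose", with the Day 85 dose given in the protocol and in SAP 5.1.

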18.2. MISSING DATA METHODS

Missing pharmacokinetic data will not be imputed. Further discussion of treatment of missing data is dealt in Section 18.1.2

18.3. DEVIATIONS RELATED TO PK

Changes to the procedures or events which may impact the quality of the PK data, that will be considered significant with respect to PK will be described within the clinical study report body text. These changes or events include any circumstances that could alter the evaluation of the PK. Examples include, but may not be limited to, sample processing errors that lead to inaccurate bioanalytical results, and/or inaccurate or missed dosing on or before the day of PK sampling. In the case of a significant PD or event, PK data collected during the affected time period will be excluded from the study summaries.

Other changes to the procedures or events which do not impact the quality of the PK data will not be considered significant with respect to PK.

